2. To determine the **efficacy** of iron supplementation among pregnant Tanzanian women, on the **incidence of low birth weight,** compared to placebo.

3. To determine the **efficacy** of iron supplementation among pregnant Tanzanian women, on the **incidence of maternal malaria infection,** compared to placebo.

4. To determine the **efficacy** of iron supplementation among pregnant women on **infant hemoglobin concentrations at 6 weeks**, compared to placebo.

5. To determine the **efficacy** of iron supplementation among pregnant Tanzanian women on **infant malaria parasitemia at 6 weeks**, compared to placebo.

6. To determine the **adherence** to iron supplementation intake by pregnant women compared to placebo.

Background and Significance

Burden of Iron Deficiency

Iron deficiency is the most common form of anemia worldwide; approximately 50% of anemia is attributable to iron deficiency [16-18]. Iron deficiency has a detrimental impact on human health, nutrition, and socioeconomic development. Globally, iron deficiency accounts for 841,000 deaths and 35,057,000 disability-adjusted life years lost, and ranks ninth globally among the 26 leading risk factors worldwide [19]. Pregnant women are particularly vulnerable to iron deficiency and anemia, and anemia is the most common medical disorder in pregnancy. Approximately 41.8% of pregnant women (56 million) are anemic worldwide [1], with iron deficiency anemia accounting for the majority of cases. Anemia has been related to increased maternal morbidity and mortality and adverse perinatal outcomes [20-27] and reduced cognitive development and functioning [28-30] and work capacity [30, 31]. Iron deficiency anemia is a severe public health problem in malaria-endemic countries of Africa. Approximately 17.2 million pregnant women and 83.5 million children under five are anemic in sub-Saharan Africa [1]. Iron deficiency contributes to 22% of all maternal mortality (30-44 years), and 33% of all perinatal mortality [32].

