Laboratory Investigations: A peripheral venous blood sample of 10 ml will be taken from all women at screening, 20 weeks, 30 weeks, delivery, and 6 weeks post-partum. At screening, blood will be tested for a complete blood count and serum ferritin. Following randomization, the following additional assessments will be performed: ABO blood typing as part of standard prenatal care, a sickling test, a blood smear for malaria parasitemia, and c-reactive protein. Malaria parasitemia during pregnancy will be further assessed before ingestion of SP intermittent preventive therapy at 20 and 30 weeks of gestation. At delivery, the following laboratory assessments will be performed in mothers: serum ferritin, c-reactive protein, a complete blood count, and malaria parasitemia. A cord blood specimen and a placental blood specimen from drained retroplacental blood will also be collected at delivery. At the 6 week post-partum visit, malaria parsitemia will be assessed in mothers and a 1 ml specimen will be drawn from the infants through venipuncture for a peripheral blood smear for malaria and a complete blood count. If venipuncture is unsuccessful, however, the heel stick method will be used as an alternative.

Peripheral thick blood smears will be stained with Giemsa and then examined for parasites. Parasite species and density will be recorded. The presence or absence of asexual forms of parasites will be recorded, and the density of such stages will be recorded. Slides will be examined without knowledge of clinical malaria status. In addition, qualitative and quantitative PCR for malaria will be performed at delivery for mothers and at 6 weeks post partum for infants.

After delivery, the placenta will be brought to the laboratory in a sealed plastic bucket containing 500 ml normal saline. A 1 cm3 biopsy will be taken from the maternal side of the placenta

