An internal medical monitor will be hired in Dar es Salaam to ensure that the study design is implemented according to protocol. S/he will be a physician with research training and will undertake regular meetings with the site coordinator and with members of the study staff; review of data collection forms and related records to assess their completeness; observation of the study personnel carrying out specific procedures; review of other documents and files at the site to assess whether they are up-to-date; physical or verbal walk-through of certain procedures; conversations with key support personnel to assess their practices with regard to data collection; and inspection of storage facilities (laboratory and data).

Definition of Main Endpoints

Primary endpoints: These will be the incidence and parasite density of placental malaria. Placental infection status will be categorized as infected if there are asexual parasites in the placenta blood; not infected if the placental blood smear is negative; or status unknown if no placental smear is available. Placental malaria parasite density will be defined as number of parasites per μ L of blood or 200 white blood cells; the latter will be converted to a count per μ L of blood assuming a count of 8000 WBC/µL [155]. The continuous measurements of maternal hemoglobin and birth weight will be two other primary endpoints.

Secondary endpoints: Low birth weight will be defined as birth weight less than 2500 grams. Maternal malaria will be defined in 2 ways: fever within the last 72 hours with any parasitemia on a peripheral blood smear. High density malaria will be defined as fever with parasitemia >5000. Anemia will be defined as hemoglobin less than 11 g/dl. Severe anemia is less than 8.5 g/dl.

Data Analysis

Analysis of primary endpoints: Intent-to-treat analysis of treatment effects will be used as the primary analysis strategy for all endpoints.

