Birth Weight: The difference between mean birth weights in the iron and placebo arms will be calculated, and the statistical significance of any observed difference will be assessed by a two-sample t-test and non-parametrically by a Wilcoxon rank-sum test. A linear regression model will be used to adjust for residual treatment imbalances by risk factors, and to evaluate effect modification by these risk factors, using the methods for multivariate modeling described above.

Analysis of Secondary Endpoints

Low Birth Weight (<2500 g): Analyses of the effects of iron supplements on low birth weight will parallel those outlined above for placental malaria infection, also a binary endpoint.

Maternal anemia (Hb < 11.0 g/dL) and Maternal malaria infection: These binary secondary endpoints, as noted in the Definition of Endpoints section, will be analyzed in a similar fashion as the primary endpoints as described above, although only women without these conditions at baseline will contribute to these analyses.

Analysis of Adherence and Iron Status Biomarkers: Pill counts will be undertaken at monthly clinic visits. Serum concentrations of ferritin will be assessed on all subjects at baseline and among a subset of 300 women at delivery. Increased intake of iron is usually paralleled by increases in serum ferritin values, and concentrations of serum ferritin and pill counts will be compared between the active treatment and placebo arms as proxy indicators for adherence with the supplements. The analysis will be based on a regression model for the change from baseline to delivery and supplemented by Wilcoxon rank-sum tests. Median changes (and associated order-statistic-based 95% CI's) will be summarized by treatment arm. The effect of iron supplementation on serum transferrin receptor, hepcidin, and C-reactive protein will be also examined, following a similar approach.

Statistical Power Calculations

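### Secondary aim 3 is about maternal malaria infection, but every printed definition of maternal malaria requires fever, so the endpoint as written measures febrile malaria

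*Protocol*

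**What the plan says.** Specific Aims, Secondary Aims, item 3, names the "incidence of maternal malaria infection" as the outcome, iron against placebo.

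Definition of Main Endpoints, Secondary endpoints, gives the definition: "Maternal malaria will be defined in 2 ways: fever within the last 72 hours with any parasitemia on a peripheral blood smear". The following sentence reads: "High density malaria will be defined as fever with parasitemia >5000". It gives no unit for the threshold.

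Analysis of Secondary Endpoints has an entry headed with maternal anemia and maternal malaria infection. It says: "These binary secondary endpoints, as noted in the Definition of Endpoints section, will be analyzed in a similar fashion as the primary endpoints", and it restricts the risk set: "although only women without these conditions at baseline will contribute to these analyses". It adds no definition of its own.

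Laboratory Investigations describes smears taken whether or not the woman is ill: "Malaria parasitemia during pregnancy will be further assessed before ingestion of SP intermittent preventive therapy at 20 and 30 weeks of gestation". The schedule table lists maternal smears at enrolment, 20 weeks, 30 weeks, delivery and 6 weeks postpartum. For each smear, "The presence or absence of asexual forms of parasites will be recorded, and the density of such stages will be recorded". Maternal PCR for malaria is added at delivery.

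**The concern.** The aim and the analysis heading use the word infection. The definitions they depend on describe an illness: parasites together with fever. The two are different outcomes, because infection includes women who carry parasites without fever.

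Two consequences follow. Parasitaemia without fever, found on a scheduled smear after randomisation, does not count towards the endpoint meant to answer aim 3. The same definition also decides who is free of the condition at baseline, so a woman with parasites but no fever at randomisation is kept as at risk. If she later has fever with parasites she becomes an incident case, although infection was documented before treatment began.

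The trial asks whether iron changes malaria risk. A null finding on this endpoint would be reported under an aim worded as infection when only febrile malaria had been compared.

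**Working it through.** The core of the check is textual.

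| Place in the protocol | Outcome described | Fever required? |
|---|---|---|
| Secondary aim 3 | Maternal malaria infection | Not mentioned |
| Background, burden of malaria | Maternal malaria infection as peripheral or placental infection (median prevalence 27.8%) | No |
| Primary endpoint, placental infection | Asexual parasites in placental blood | No |
| Secondary endpoint, maternal malaria | Any parasitaemia on a peripheral smear | Yes, within 72 hours |
| Secondary endpoint, high density malaria | Parasitaemia above 5000, no unit | Yes |
| Analysis of Secondary Endpoints | Refers back to the endpoint definitions | Inherits the requirement |

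Applying the printed rules to individual women:

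- Positive scheduled smear after randomisation, no fever: meets neither definition, scored as a non-case.
- Positive smear at randomisation, no fever: does not have the condition at baseline, so she remains in the risk set.
- The second woman, later febrile with parasites: scored as an incident case.

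**Illustration of size.** The power section covers only the primary aims, so there is no stated figure to reproduce. Inputs:

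- Women per arm: 1500 × 0.90 / 2 = 675, using the protocol's 10% loss allowance and assuming equal arms.
- Two-sided alpha 0.05, from the power section.
- Placebo risk of infection: the Kenyan study in the Background reports peripheral malaria in 23% of primigravidae and 18% of secundigravidae. An equal mix gives (23 + 18) / 2 = 20.5%. This is a cross-sectional prevalence used as a stand-in for incidence.
- Relative risk 1.3, chosen for illustration.
- Febrile share of infections: not in the protocol. Assumed to be 10%, 25% or 50%.

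Formula, with p1 the placebo risk, p2 = 1.3 × p1, p̄ their mean and n = 675:

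se0 = √[2p̄(1 − p̄)/n], se1 = √[(p1(1 − p1) + p2(1 − p2))/n], power = Φ[(p2 − p1 − 1.96·se0)/se1].

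For all infections: p1 = 0.205, p2 = 0.2665, se0 = 0.02311, se1 = 0.02304. Power = Φ[(0.0615 − 0.0453)/0.02304] = Φ(0.70) = 76%.

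| Infections counted | Placebo risk | Placebo events (675 × risk) | Power |
|---|---|---|---|
| All | 20.5% | 138 | 76% |
| 50% | 10.25% | 69 | 42% |
| 25% | 5.1% | 35 | 22% |
| 10% | 2.05% | 14 | 11% |

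Starting from the Background's 27.8% instead, the same calculation gives 91% when all infections count, and 55%, 29% and 14% at febrile shares of 50%, 25% and 10%.

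**Effect of the corrected baseline rule.** Women who are smear-positive at baseline would leave the risk set for the infection endpoint. If 20.5% were positive at baseline, 675 × 0.795 = 537 per arm would remain. With p1 still 20.5%, se0 = 0.02591 and se1 = 0.02584, so power = Φ[(0.0615 − 0.0508)/0.02584] = Φ(0.42) = 66%. This too is only an indication: risk among women negative at baseline may be lower, while repeated smears would raise cumulative incidence.

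**The case against.** The strongest objection is that the text may simply be incomplete. Two definitions are promised and only one follows the colon. High density malaria is defined in its own sentence under its own name, so it is not certain that it is the second of the two. A fever-free definition may have been lost in editing. This stands as a caution against calling the two definitions settled. It does not remove the problem: no fever-free definition is printed, and the analysis section relies on what is printed.

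A reader might infer that aim 3 cannot be answered. The documents do not support that. Smears are scheduled for all women, presence and density of parasites are recorded, and PCR is done at delivery. The fault lies in the definition, not in data capture, and the endpoint as written still answers a narrower question.

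A reader might also take this for the trial's main maternal safety outcome after the placenta. The protocol does not say so. Safety is primary aim 1, on placental malaria; maternal malaria infection is listed as a secondary efficacy aim. The primary placental endpoint carries no fever condition.

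It would also go too far to say that most smear information is discarded or that only febrile episodes near a scheduled visit count. The first depends on a febrile share the protocol does not give. On the second, women may attend the study clinic at any time, and the protocol does not say whether smears from such attendances count.

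Finally, the power figures rest on an assumed febrile share, a prevalence used as incidence, and the same relative effect on febrile and afebrile infection. They contradict no stated figure. All of this stands, and they are offered only as illustration. The baseline point is a consequence of the mismatch, not a second error: for a clinical malaria endpoint, a later febrile episode in a woman parasitaemic at baseline is a legitimate new event.

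**Conclusion.** The mismatch is real and lies in what the protocol states, not in detail left for an analysis plan. Aim 3 and the analysis heading concern infection; every printed definition of maternal malaria requires fever; and the announced pair of definitions is incomplete. As written, the endpoint measures febrile malaria, leaves out parasitaemia without fever, and keeps women who are parasitaemic but afebrile at randomisation in the risk set. A null result could then be misread as no effect on infection.

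That conclusion needs no numerical assumption beyond some infections occurring without fever. The size does: at 675 per arm, 20.5% infection risk and relative risk 1.3, an assumed febrile share of 10–50% takes power from about 76% to 11–42%. The endpoint is secondary, so this should be corrected but does not threaten the primary analyses.

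**What to change.** In Definition of Main Endpoints, define maternal malaria infection for aim 3 as asexual parasites of any density on a peripheral smear, regardless of fever. In Analysis of Secondary Endpoints, apply that same definition when deciding who is free of the condition at baseline for this endpoint. Keep fever with parasitaemia (clinical malaria) and high density malaria as separately named endpoints, and give the unit for the 5000 threshold. If a second definition was dropped from the text, restore it at the same time.

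The cost is about one sentence in the endpoint definitions and a matching phrase in the analysis section. No visit, sample or test is added, because the smears are already scheduled and read with density recorded. The small downside is that women who are smear-positive at baseline leave the risk set for the infection endpoint.

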
Experimental Regimens and Randomization Procedures: Women will be randomly assigned to receive a daily oral dose of one of the following two regimens from enrollment and until delivery: (a) 60 mg iron (as ferrous sulphate) or (b) placebo. Tablets will be packaged in identical coded bottles that contain supply for 45 days (although the research visits are scheduled at monthly intervals, the extra tablets are necessary in case a woman is delayed in coming in for her scheduled visit). A list from 1 to 1500 will be prepared according to a randomization sequence in blocks of 20. Each of the two study clinics where randomization will occur will have a subset of the list of numbers. At enrollment, each eligible woman will be assigned to the next numbered bottle of regimen at that site. Experience has shown that unblinding, whether real or based on an impression or perception that develops among subjects or staff, is more likely to occur if regimens are color-coded or bear simple numeric codes. To minimize this risk, we will provide the regimen in bottles labeled with the participant's identification numbers, and will make active tablets and placebo indistinguishable, so that neither the subjects nor the investigators can identify which group of subjects is randomized to the same regimen.

The proposed dose of 60 mg elemental iron (200 μ g ferrous sulphate) is the WHO-recommended dose for universal supplementation during pregnancy. It also corresponds to the WHO-recommended dose for daily supplementation over a 3-month period among lactating women and women of reproductive age who live in areas where the prevalence of anemia exceeds 40% [84]. Although the prevalence of anemia among women of reproductive age exceeds 40% in Tanzania [33], the WHO-guidelines during lactation and reproductive age have not been adopted by the Tanzanian Ministry of Health and this practice is thus currently not in use [84].

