Placental Malaria Infection: We will compare the proportions of randomized women who have placental malaria infection in the iron group, compared with women on placebo. To test the statistical significance of any difference observed we will use the χ^2 test. There are numerous risk factors for placental malaria which will be measured in this study at baseline (defined as the time of randomization), including maternal body mass index, gravidity, maternal mid upper arm circumference, hemoglobin, gestational age, maternal age, parity, and indicators of socioeconomic status as measured by education, occupation, possessions, and marital status. Although randomization ensures that, on average, treatment groups will be balanced with respect to all of these risk factors, this may not be true in the particular instance of the current study. Thus, we wish to assess the success of randomization by first comparing the baseline characteristics of women in the treatment groups using χ^2 and t-tests and then using multivariate modeling techniques such as logistic regression to identify the strongest independent imbalances. Then, we will re-assess treatment effects as observed in the original intent to treat analysis after adjusting for the risk factors associated with the strongest imbalances. A logistic regression model will be used for this analysis. We will compare treatment effects estimated from the original analysis to those obtained from the adjusted analysis to decide whether adjustment is necessary. Because placental malaria is not likely to be a rare event in this study population, the odds ratio may not be a good approximation to the parameter of interest, the risk ratio. Multivariate regression models for the risk ratio are now available in commercial software, and we will apply binomial regression models with the log and identity link functions to the data as well. Linearity of multiple risk factors on one scale, e.g. the logistic, generally implies that there will be interactions of these risk factors on another scale, e.g. with the identity link. Goodness-of-fit of the data to various models forms will be explored, and interactions reported.

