Power for the primary aims, placental malaria infection and density, maternal hemoglobin levels, and birth weight, have been calculated based on a nominal Type I error rate (alpha) of 0.05, and a 10% sample size adjustment for loss-to-follow-up and fetal loss. Power is based on a 2-sided test of proportions, based on a Z-statistic using the asymptotic variances of the observed proportions. The table below displays the power of the study to detect treatment effects on placental malaria infection. The assumed placebo arm rate of 20-30% is supported by studies reviewed above [37, 39]. Displayed is the power (for treatment effects expressed as % reductions) based on a 2-sided test for comparison of proportions, total enrolled n=1500, with a 10% sample size adjustment to account for loss to follow-up and fetal loss.

Statistical Power for Incidence of Placental Malaria							
Incidence in Placebo Arm	Effect of Intervention on the Incidence						
	HR=0.75	HR=0.70	HR=0.65	HR=0.60			
20%	48%	65%	80%	90%			
25%	57%	74%	87%	95%			
30%	64%	80%	92%	98%			

The study will have good power to detect a 35% effect size, for placental malaria rates as low as 20% in the placebo arm. If the placental malaria rates are larger (25% or 30%), the study will have good power to detect a 30% effect size and excellent power to detect a 40% effect size.

Continuous Variables: The table below displays the power of the study to detect treatment effects on continuous variables, including placental malaria density, maternal hemoglobin concentration, and birth weight. Displayed is the power (for treatment effects expressed as percent changes in effect size) based on a 2-sided test for comparison of proportions, total enrolled n=1500, with a 10% sample size adjustment to account for loss to follow-up.

Placental malaria density: The table below displays the power of the study to detect treatment effects on placental malaria density. The assumed mean placental malaria density in the placebo arm of 9,000 parasites/ μ L is supported by studies reviewed above [156]. The study will have good power to detect an effect size of 8.5%, and excellent power to detect a 10-20% change, based on a 2-sided test for comparison of proportions, total enrolled n=1500, with a 10% sample size adjustment to account for loss to follow-up and fetal loss. The study will have good power to detect an 8.5% effect size, and excellent power to detect an effect size of 10% or greater.

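### Placental malaria: covariates are chosen by baseline imbalance, and the need for adjustment is decided after seeing both treatment effects, with no criterion and no final estimate named

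*Protocol*

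**What the plan says.** Under Analysis of primary endpoints, the protocol makes intention to treat the primary strategy for every endpoint. Under Placental Malaria Infection it then sets out this sequence:

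1. Compare the proportions infected by a chi-square test.
2. Compare baseline characteristics between arms by chi-square and t-tests, and use a multivariable model to find the strongest independent imbalances. The candidates are introduced by the word *including*: seven clinical factors (body mass index, gravidity, mid-upper arm circumference, hemoglobin, gestational age, maternal age, parity) and four socioeconomic indicators (education, occupation, possessions, marital status).
3. Re-assess the treatment effect by logistic regression, "adjusting for the risk factors associated with the strongest imbalances".
4. Decide: "We will compare treatment effects estimated from the original analysis to those obtained from the adjusted analysis to decide whether adjustment is necessary".
5. Because the outcome is not rare and the risk ratio is the quantity wanted, also fit binomial models with log and identity links. "Goodness-of-fit of the data to various models forms will be explored, and interactions reported".

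Other endpoints reuse parts of this:

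- **Parasite density and hemoglobin:** regression adjusts for factors left imbalanced after randomisation. The decision step is not repeated.
- **Birth weight:** "A linear regression model will be used to adjust for residual treatment imbalances by risk factors", with a reference back to the modelling methods above.
- **Low birth weight, maternal anemia and maternal malaria:** analysed in parallel with the primary endpoints.

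**The concern.** There are two faults in the rule as written.

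**The selector is wrong.** In a randomised trial a baseline difference is due to chance by design, so its p-value says nothing about whether the factor predicts placental malaria. A strong predictor that happens to be balanced is left out, and a weak one that happens to be imbalanced is brought in.

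**The decision comes too late.** Whether adjustment is needed is judged by looking at the two treatment effects. No size of change, number of covariates or imbalance threshold is given, and nothing says which estimate stands when they differ. Two analysts could follow the text faithfully and report different effects of iron on the primary safety endpoint.

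The comparison is also a poor guide in itself. The adjusted model is logistic, and an odds ratio moves when a prognostic factor is added even if the arms are perfectly balanced on it. A shift therefore does not show that imbalance needed correcting.

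**Working it through.** The plan attaches no figure to the adjustment rule, so there is none to reproduce. The checks below size its consequences.

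**Inputs from the protocol**

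- Type I error: "based on a nominal Type I error rate (alpha) of 0.05".
- Sample: "total enrolled n=1500, with a 10% sample size adjustment to account for loss to follow-up and fetal loss". This gives 1500 × 0.90 = 1350 evaluable women, or 675 per arm.
- Allocation: "A list from 1 to 1500 will be prepared according to a randomization sequence in blocks of 20". A 1:1 ratio is assumed, as none is stated.
- Placebo-arm rate of placental malaria: 20–30%.
- Candidate factors: 7 + 4 = 11.

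**Check 1: chance imbalance.** Assume a p<0.05 threshold and independent factors. P(at least one imbalanced) = 1 − 0.95^11 = 1 − 0.569 = 0.431, about 43%. Correlated factors lower this, and gravidity and parity clearly overlap.

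**Check 2: type I error.** The simulation used 1350 women, a base risk of about 20%, 11 independent standard-normal covariates and 15,000 null replicates per row. The adjusted model takes the two most imbalanced covariates. The protocol gives no switching threshold, so the switch rule assumes a move to the adjusted result when the log odds ratio changes by more than 10%.

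| Covariate log OR per SD | Unadjusted | Switch at 10% | More favourable of the two |
|---|---|---|---|
| 0.10 | 4.9% | 5.0% | 5.4% |
| 0.25 | 5.0% | 4.5% | 5.8% |
| 0.40 | 4.8% | 4.0% | 5.9% |

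A neutral switch does not inflate the error. Always taking the more favourable result does, by about 0.4 to 0.9 points above 5%. The switch rule chose the adjusted result in 56%, 72% and 77% of these null trials, so the assumed rule would often change the reported number.

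**Check 3: power under the rule.** With a treatment OR of 0.65 and covariate log OR 0.25 (5,000 replicates), power was 79.9% unadjusted, 81.3% with the switch and 83.1% taking the more favourable result.

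**Check 4: what fixed adjustment could add.** Take one binary prognostic factor with assumed prevalence 5–20% and assumed OR 2–5 for the outcome, at a placebo rate of 20–30%. Approximate the standard-error ratio by √(1 − R²).

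- R² runs from 0.5% to 10%, giving ratios of √0.995 = 0.997 to √0.90 = 0.949.
- A design with 80% power has power Φ((1.96 + 0.84)/√(1 − R²) − 1.96), which is 80.2% at R² = 0.5% and 84.0% at R² = 10%.
- In a separate simulation with all 11 covariates fixed in advance and an OR of about 0.60, power was 92.5% against 90.1% unadjusted.

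The gain is therefore roughly 0 to 4 points.

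**Check 5: movement of the odds ratio without imbalance.** Take a perfectly balanced factor with prevalence 10–18% and outcome OR 2–5 (assumed), a placebo rate of 20–30% and a treatment OR of 1.45 (assumed). The log odds ratio for treatment grows by about 1% to 10% on adjustment. At the upper end this alone would reach a 10% change rule.

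**The case against.** The strongest reply is that the primary test is clear. Intention to treat is primary for all endpoints, the chi-square comes first, adjustment is described as a re-assessment, and the power section matches: "Power is based on a 2-sided test of proportions, based on a Z-statistic using the asymptotic variances of the observed proportions". This stands. A reader might infer that the trial has no pre-planned primary test; the document does not support that. What remains open is which effect estimate is relied on.

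Four other stronger readings also fail:

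- **Baseline parasitaemia was excluded.** The candidate list is open, so the smear and sickling test are unnamed, not ruled out. Nor does the protocol show that baseline parasitaemia predicts placental malaria. Its own preliminary data, in HIV-infected women, link it to severe anemia, low birth weight and weight gain. For a malaria outcome, the support it cites is for sickle trait.
- **The plan is shown to be less precise.** It is not. The possible power gain depends on assumed prevalences and odds ratios, and in logistic regression adjustment can raise power without shrinking the standard error of the log odds ratio.
- **The decision is made across three link functions.** The sentence follows the logistic model; the log and identity links are added afterwards.
- **The decision rule applies to every endpoint.** It is explicit only for placental infection. It reaches birth weight and the binary secondary endpoints by cross-reference, and is not stated for density or hemoglobin.

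It can also be said that a covariate list commonly belongs in the SAP. That would answer silence, but here the protocol states a selection rule and a decision rule, and both are unsound as stated.

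**Conclusion.** The point holds in limited form. Imbalance testing is the wrong way to choose covariates, and deciding on adjustment after comparing treatment effects leaves the estimate for the primary safety endpoint to judgement. The main cost is that discretion.

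The numerical harm is modest: up to about one percentage point of type I error, only if the more favourable result is taken, and roughly 0 to 4 points of power forgone. These sizes rest on assumed thresholds, covariate strengths, prevalences and independence. The fault in the wording does not depend on them. It should be corrected, but it does not invalidate the chi-square test.

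**What to change.** Make these changes before unblinding:

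1. Delete baseline testing as a means of choosing covariates. A descriptive baseline table can stay.
2. Delete the compare-then-decide sentence.
3. Name one primary estimate for placental malaria. The risk ratio with 95% CI fits the protocol's own stated interest.
4. Fix a short covariate set for the adjusted analysis of each endpoint from data already collected, for example gravidity, gestational age, baseline smear and sickling result, plus the baseline value of the outcome where one exists, as for hemoglobin.
5. State in advance whether the unadjusted or the fixed-covariate analysis is primary. Either is defensible; an unadjusted primary matches the stated power basis.
6. Label every other model, including the alternative links, as a sensitivity analysis.

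The cost is wording in the protocol and in any SAP. No new data, visits or participants are needed.
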